9.7.6. Safety Analysis

Not applicable.

9.8. QUALITY CONTROL

The quality control, review, and monitoring plan are summarized below. Greater details are documented in the NIS-DMRP.

NIS Protocol BI Study Number 1403-0024 Page 25 of 37 C42272174

Proprietary confidential information© 2023 Boehringer Ingelheim GmbH or one or more of its affiliated companies

The study will strictly follow key elements of the Guideline for Good Pharmacoepidemiology Practices (GPP) and other relevant standard operating procedures (SOPs). The study report will be reviewed, approved and archived per BI SOP.

One Data Analyst from will build measures (variables) for cohort inclusion and outcomes. Whenever possible, validated algorithms will be used for variables, to minimize misclassification and information bias. All measures created, cohorts developed, statistical analyses implemented, and tables output will undergo quality control review performed by at least one additional Analyst from Quality controls include checks for the validity and logical content of codes and checks for missing values and variables. In order to control for potential inconsistencies and errors, all variables will be tabulated. The distribution of each variable will be examined.

The NIS Lead will verify that the Data Analyst has followed methodology specified in the protocol, as well as any relevant programming SOPs and good programming practices. Documentation of key programming decisions should be evident within the program. The investigator or NIS Lead will verify that any assumptions made by the data analyst are consistent with expectations.

9.9. LIMITATIONS OF THE RESEARCH METHODS

There are several limitations of this study. Firstly, CDC mortality surveillance data may only capture 80% of the total deaths, which may result in over-estimate of the survival outcomes. We attempt to conduct sensitivity analyses in area with higher completeness on survival data. Still, results should be interpreted with caution.

Secondly, the study could be subjected to missing clinical information that is not routinely recorded by clinicians, variations in the reporting, and selection biases arise from the use of diagnostic and therapeutic codes. Under-reporting of comorbidities and of treatment received outside the oncology clinic setting may result in misclassification of treatments and outcomes.

Additionally, as this study population includes patients from tertiary or oncology hospitals in China, study results might not be generalizable to entire Chinese DDLPS patients. As oncology care remain only possible or most optimally delivered though face-to-face, patients' access to oncological services is possibly limited during COVID-19 pandemic impacts, consequently resulting in less patient diagnosis and hospital visits.

9.10. OTHER ASPECTS

9.10.1. Data quality assurance

A quality assurance audit/inspection of this study may be conducted by the sponsor or sponsor's designees or by Institutional Review Board (IRBs) / Independent Ethics Committee (IECs) or by regulatory authorities. The quality assurance auditor will have access to all medical records, the investigator's study-related files and correspondence of this study.

NIS Protocol BI Study Number 1403-0024 Page 26 of 37 C42272174

Proprietary confidential information© 2023 Boehringer Ingelheim GmbH or one or more of its affiliated companies

9.10.2. Study records

Not applicable.

10.PROTECTION OF HUMAN SUBJECTS

The study will be carried out in compliance with the protocol, the principles laid down in the Declaration of Helsinki, Guidelines for GPP, and the relevant BI SOPs.

10.1. STUDY APPROVAL, PATIENT INFORMATION, AND INFORMED CONSENT

This NIS will be initiated only after all required legal documentation has been reviewed and approved by the respective IRB/ IEC according to national and international regulations. The same applies for the implementation of changes introduced by amendments.

Ethical approval will be obtained prior to start of data collection. The finalized protocol will be submitted to an IRB in China for review and approval.

10.2. STATEMENT OF CONFIDENTIALITY

Individual patient medical information obtained as a result of this study is considered confidential and disclosure to third parties is prohibited with the exceptions noted below. Patient confidentiality will be ensured by using patient identification code numbers.

Only anonymized data will be used in the study. Data generated as a result of the study need to be available for inspection on request by the participating physicians, the sponsor's representatives, by the IRB/IEC and the regulatory authorities.

11. MANAGEMENT AND REPORTING OF ADVERSE EVENTS/ADVERSE REACTIONS

Not applicable based on secondary use of data without any potential that any employee of BI or agent working on behalf of BI will access individually identifiable patient data.

Based on current guidelines from the International Society for Pharmacoepidemiology and the EMA, non-interventional studies such as the one described in this study protocol, conducted using electronic claims and/or health care records, do not require expedited reporting of suspected adverse events/reactions. Specifically, as stated in section VI.C.1.2.1 of *Guideline on Good Pharmacovigilance Practices (GVP), Module VI – Management and Reporting of Adverse Reactions to Medicinal Products*, for non-interventional study designs, which are based on use of secondary data, reporting of adverse reactions is not required. In addition, this study does not involve BI product and no safety outcomes are included in the study. No BI employees will have access to the original data. As such, with no individual medical record review, the safety reporting is not applicable.

NIS Protocol BI Study Number 1403-0024 Page 27 of 37 C42272174

Proprietary confidential information© 2023 Boehringer Ingelheim GmbH or one or more of its affiliated companies

12. PLANS FOR DISSEMINATING AND COMMUNICATING STUDY RESULTS

The rights of the investigator and of the sponsor with regard to publication of the results of this study are described in the investigator contract. As a general rule, no study results should be published prior to finalization of the Study Report.

At this time, this study is planned to help inform the asset program and may be used to supplement regulatory submissions. However, it is not conducted solely for regulatory approval.

ANNEX 1. LIST OF STAND-ALONE DOCUMENTS

None.

ANNEX 2. ENCEPP CHECKLIST FOR STUDY PROTOCOLS

Study title: Demographic, clinical characteristics, and treatment outcomes associated with dedifferentiated liposarcoma patients in China

EU PAS Register® number: Study reference number (if applicable):					
Sect	ion 1: Milestones	Yes	No	N/A	Section Number
1.1	Does the protocol specify timelines for				
	1.1.1 Start of data collection ¹				
	1.1.2 End of data collection ²				6
	1.1.3 Progress report(s)				
	1.1.4 Interim report(s)				
	1.1.5 Registration in the EU PAS Register®				
	1.1.6 Final report of study results.				
Comn	nents:				
Sect	ion 2: Research question	Yes	No	N/A	Section
500.		. 03	.,,	11,71	Number
2.1	Does the formulation of the research question and objectives clearly explain:	\boxtimes			
	2.1.1 Why the study is conducted? (e.g. to address an important public health concern, a risk identified in the risk management plan, an emerging safety issue)				7
	2.1.2 The objective(s) of the study?				8
	2.1.3 The target population? (i.e. population or subgroup to whom the study results are intended to be generalised)	\boxtimes			9.2.2,9.7.4
	2.1.4 Which hypothesis(-es) is (are) to be tested?				
	2.1.5 If applicable, that there is no a priori hypothesis?	\boxtimes			9.1, 9.3
Com n	nents:				

¹ Date from which information on the first study is first recorded in the study dataset or, in the case of secondary use of data, the date from which data extraction starts. ² Date from which the analytical dataset is completely available.

NIS Protocol BI Study Number 1403-0024 Page 30 of 37 C42272174

Sect	ion 3: Study design	Yes	No	N/A	Section Number
3.1	Is the study design described? (e.g. cohort, case-control, cross-sectional, other design)	\boxtimes			9.1
3.2	Does the protocol specify whether the study is based on primary, secondary or combined data collection?	\boxtimes			9.1, 9.2
3.3	Does the protocol specify measures of occurrence? (e.g., rate, risk, prevalence)	\boxtimes			9.3.1
3.4	Does the protocol specify measure(s) of association? (e.g. risk, odds ratio, excess risk, rate ratio, hazard ratio, risk/rate difference, number needed to harm (NNH))				
3.5	Does the protocol describe the approach for the collection and reporting of adverse events/adverse reactions? (e.g. adverse events that will not be collected in case of primary data collection)				9.3.1
Comn	nents:				
Sect	ion 4: Source and study populations	Yes	No	N/A	Section Number
4.1	Is the source population described?				9.4
4.2	Is the planned study population defined in terms of:				9.2
	4.2.1 Study time period	\boxtimes			
	4.2.2 Age and sex				
	4.2.3 Country of origin				
	4.2.4 Disease/indication				
	4.2.5 Duration of follow-up				
4.3	Does the protocol define how the study population will be sampled from the source population? (e.g. event or inclusion/exclusion criteria)				9.2
Comn	nents:				
					_
	ion 5: Exposure definition and surement	Yes	No	N/A	Section Number
5.1	Does the protocol describe how the study exposure is defined and measured? (e.g. operational details for defining and categorising exposure, measurement of dose and duration of drug exposure)				
5.2	Does the protocol address the validity of the exposure measurement? (e.g. precision, accuracy, use of validation sub-study)			\boxtimes	

NIS Protocol BI Study Number 1403-0024 Page 31 of 37 C42272174

	ion 5: Exposure definition and surement	Yes	No	N/A	Section Number
5.3	Is exposure categorised according to time windows?				
5.4	Is intensity of exposure addressed? (e.g. dose, duration)				
5.5	Is exposure categorised based on biological mechanism of action and taking into account the pharmacokinetics and pharmacodynamics of the drug?				
5.6	Is (are) (an) appropriate comparator(s) identified?			\boxtimes	
Comn	nents:				
	ion 6: Outcome definition and surement	Yes	No	N/A	Section Number
6.1	Does the protocol specify the primary and secondary (if applicable) outcome(s) to be investigated?	\boxtimes			9.3.1
6.2	Does the protocol describe how the outcomes are defined and measured?				9.3.1
6.3	Does the protocol address the validity of outcome measurement? (e.g. precision, accuracy, sensitivity, specificity, positive predictive value, use of validation sub-study)				
6.4	Does the protocol describe specific outcomes relevant for Health Technology Assessment? (e.g. HRQoL, QALYS, DALYS, health care services utilisation, burden of disease or treatment, compliance, disease management)	\boxtimes			9.3.1
Comn	nents:				
Sect	ion 7: Bias	Yes	No	N/A	Section Number
7.1	Does the protocol address ways to measure confounding? (e.g. confounding by indication)				
7.2	Does the protocol address selection bias? (e.g. healthy user/adherer bias)				9.9
7.3	Does the protocol address information bias? (e.g. misclassification of exposure and outcomes, timerelated bias)	\boxtimes			9.9
Comn	nents:				

NIS Protocol BI Study Number 1403-0024 Page 32 of 37 C42272174

Sect	ion 8: Effect measure modification	Yes	No	N/A	Section Number
8.1	Does the protocol address effect modifiers? (e.g. collection of data on known effect modifiers, subgroup analyses, anticipated direction of effect)				9.7.4
Comm	ients:				
Sect	ion 9: Data sources	Yes	No	N/A	Section Number
9.1	Does the protocol describe the data source(s) used in the study for the ascertainment of:				9.3
	9.1.1 Exposure? (e.g. pharmacy dispensing, general practice prescribing, claims data, self-report, face-to- face interview)			\boxtimes	
	9.1.2 Outcomes? (e.g. clinical records, laboratory markers or values, claims data, self-report, patient interview including scales and questionnaires, vital statistics)				
	9.1.3 Covariates and other characteristics?				
9.2	Does the protocol describe the information available from the data source(s) on:				9.4
	9.2.1 Exposure? (e.g. date of dispensing, drug quantity, dose, number of days of supply prescription, daily dosage, prescriber)				
	9.2.2 Outcomes? (e.g. date of occurrence, multiple event, severity measures related to event)	\boxtimes			
	9.2.3 Covariates and other characteristics? (e.g. age, sex, clinical and drug use history, comorbidity, co-medications, lifestyle)				
9.3	Is a coding system described for:				
	9.3.1 Exposure? (e.g. WHO Drug Dictionary, Anatomical Therapeutic Chemical (ATC) Classification System)				
	9.3.2 Outcomes? (e.g. International Classification of Diseases (ICD), Medical Dictionary for Regulatory Activities (MedDRA))			\boxtimes	
	9.3.3 Covariates and other characteristics?				
9.4	Is a linkage method between data sources described? (e.g. based on a unique identifier or other)			\boxtimes	
Comm	ients:				
Sect	ion 10: Analysis plan	Yes	No	N/A	Section Number
10.1	Are the statistical methods and the reason for their choice described?	\boxtimes			9.7
10.2	Is study size and/or statistical precision estimated?				9.7

NIS Protocol BI Study Number 1403-0024 Page 33 of 37 C42272174

	Fricary confidential information 2023 Boeininger ingenienn Ginor			1	1
Sect	ion 10: Analysis plan	Yes	No	N/A	Section Number
10.3	Are descriptive analyses included?	\boxtimes			9.7
10.4	Are stratified analyses included?			\boxtimes	
10.5	Does the plan describe methods for analytic control of confounding?				
10.6	Does the plan describe methods for analytic control of outcome misclassification?	\boxtimes			9.7
10.7	Does the plan describe methods for handling missing data?				9.7
10.8	Are relevant sensitivity analyses described?				9.7
Comm	ents:				
Sect cont	ion 11: Data management and quality rol	Yes	No	N/A	Section Number
11.1	Does the protocol provide information on data storage? (e.g. software and IT environment, database maintenance and anti-fraud protection, archiving)			\boxtimes	
11.2	Are methods of quality assurance described?	\boxtimes			9.8
11.3	Is there a system in place for independent review of study results?				
Comm	ents:				
Sect	ion 12: Limitations	Yes	No	N/A	Section Number
12.1	Does the protocol discuss the impact on the study results of:				
	12.1.1 Selection bias?	\boxtimes			9.9
	12.1.2 Information bias?	\boxtimes			9.9
	12.1.3 Residual/unmeasured confounding? (e.g. anticipated direction and magnitude of such biases, validation sub-study, use of validation and external data, analytical methods).				
12.2	Does the protocol discuss study feasibility? (e.g. study size, anticipated exposure uptake, duration of follow-up in a cohort study, patient recruitment, precision of the estimates)	\boxtimes			9.2, 9.5
Comm	ents:				
Sect	ion 13: Ethical/data protection issues	Yes	No	N/A	Section Number
13.1	Have requirements of Ethics Committee/ Institutional Review Board been described?	\boxtimes			10

NIS Protocol BI Study Number 1403-0024 Page 34 of 37 C42272174

Proprietary confidential information© 2023 Boehringer Ingelheim GmbH or one or more of its affiliated companies

1 ,				
Section 13: Ethical/data protection issues	Yes	No	N/A	Section Number
13.2 Has any outcome of an ethical review procedure been addressed?			\boxtimes	
13.3 Have data protection requirements been described?	\boxtimes			10
Comments:				
	1		I I	
Section 14: Amendments and deviations	Yes	No	N/A	Section Number
14.1 Does the protocol include a section to document amendments and deviations?				Annex 1
Comments:				
	1.7			
Section 15: Plans for communication of study results	Yes	No	N/A	Section Number
15.1 Are plans described for communicating study results (e.g. to regulatory authorities)?				12
15.2 Are plans described for disseminating study results externally, including publication?	\boxtimes			12
Comments:				
Name of the main author of the protocol:				
Date:				
Signature:				

ANNEX 3. ADDITIONAL INFORMATION

Charlson Comorbidity Index					
Condition	ICD-9	ICD-10			
Myocardial infarction	410.x, 412.x	I21.x, I22.x, I25.2			
Congestive heart failure	398.91, 402.01, 402.11, 402.91, 404.01, 404.03, 404.11, 404.13, 404.91, 404.93, 425.4–425.9, 428.x	I09.9, I11.0, I13.0, I13.2, I25.5, I42.0, I42.5–I42.9, I43.x, I50.x, P29.0			
Peripheral vascular disease	093.0, 437.3, 440.x, 441.x, 443.1– 443.9, 47.1, 557.1, 557.9, V43.4	I70.x, I71.x, I73.1, I73.8, I73.9, I77.1, I79.0, I79.2, K55.1, K55.8, K55.9, Z95.8, Z95.9			

NIS Protocol BI Study Number 1403-0024

Page 35 of 37 C42272174

Proprietary confidential information© 2023 Boehringer Ingelheim GmbH or one or more of its affiliated companies

Cerebrovascular disease	362.34, 430.x–438.x	G45.x, G46.x, H34.0, I60.x–I69.x
Dementia	290.x, 294.1, 331.2	F01.x–F03.x, F05.1, G30.x, G31.1
Chronic pulmonary disease	416.8, 416.9, 490.x–505.x, 506.4, 508.1, 508.8	I27.8, I27.9, J40.x–J47.x, J60.x– J67.x, J68.4, J70.1, J70.3
Rheumatic disease	446.5, 710.0–710.4, 714.0–714.2, 714.8, 725.x	M05.x, M06.x, M31.5, M32.x- M34.x, M35.1, M35.3, M36.0
Peptic ulcer disease	531.x-534.x	K25.x–K28.x
Mild liver disease	070.22, 070.23, 070.32, 070.33, 070.44, 070.54, 070.6, 070.9, 570.x, 571.x, 573.3, 573.4, 573.8, 573.9, V42.7	B18.x, K70.0–K70.3, K70.9, K71.3–K71.5, K71.7, K73.x, K74.x, K76.0, K76.2–K76.4, K76.8, K76.9, Z94.4
Diabetes without chronic complication	250.0–250.3, 250.8, 250.9	E10.0, E10.1, E10.6, E10.8, E10.9, E11.0, E11.1, E11.6, E11.8, E11.9, E12.0, E12.1, E12.6, E12.8, E12.9, E13.0, E13.1, E13.6, E13.8, E13.9
Diabetes with chronic complication	250.4–250.7	E10.2–E10.5, E10.7, E11.2– E11.5, E11.7, E12.2–E12.5, E12.7, E13.2–E13.5, E13.7
Hemiplegia or paraplegia	334.1, 342.x, 343.x, 344.0–344.6, 344.9	G04.1, G11.4, G80.1, G80.2, G81.x, G82.x, G83.0–G83.4, G83.9
Renal disease	403.01, 403.11, 403.91, 404.02, 404.03, 404.12, 404.13, 404.92, 404.93, 582.x, 583.0–583.7, 585.x, 586.x, 588.0, V42.0, V45.1, V56.x	112.0, 113.1, N03.2–N03.7, N05.2–N05.7, N18.x, N19.x, N25.0, Z49.0–Z49.2, Z94.0, Z99.2
Any malignancy	140.x-172.x, 174.x-195.8, 200.x- 208.x, 238.6	C00.x-C26.x, C30.x-C34.x, C37.x-C41.x, C43.x, C45.x- C58.xx, C60.x-C76.x, C81.x- C85.x, C88.x, C90.x-C97.x
Moderate or severe liver disease	456.0–456.2, 572.2–572.8	I85.0, I85.9, I86.4, I98.2, K70.4, K71.1, K72.1, K72.9, K76.5, K76.6, K76.7
Metastatic solid tumor	197.x-198.x	C78.xx, C79.xx, C7B.xx
AIDS/HIV	042.x-044.x	B20.x

Abbreviations: AIDS = acquired immune deficiency syndrome; HIV = human immunodeficiency virus; ICD-9-CM = International Classification of Diseases, Ninth Revision, Clinical Modification; ICD-10-CM = International Classification of Diseases, 10th Revision, Clinical Modification

NIS Protocol BI Study Number 1403-0024 Page 36 of 37 C42272174

Proprietary confidential information© 2023 Boehringer Ingelheim GmbH or one or more of its affiliated companies

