7. RATIONALE AND BACKGROUND

Liposarcoma is a malignancy of fat tissue and is one of the most commonly occurring types of soft tissue sarcoma, a heterogeneous group of rare malignancies with over 150 different histological subtypes. Liposarcomas have several forms based on clinical presentation, severity, genetic abnormality, and preferred treatment regimens [R23-1186] [R22-3794]. In 2020, the World Health Organization, reclassified liposarcomas into the following distinct categories: atypical lipomatous tumor/well-differentiated liposarcoma; myxoid liposarcoma; pleomorphic liposarcoma; myxoid pleomorphic liposarcoma; and dedifferentiated liposarcoma (DDLPS), which represents 15-20% of all liposarcoma cases [R23-1182].

DDLPS is characterized by amplification of the mouse double minute 2 homolog (MDM2) gene. MDM2 is a negative regulator of tumor protein 53 (TP53) [P20-03237]. There are few published epidemiological studies of DDLPS with quite limited incidence and prevalence data. According to an internal BI analysis of Surveillance, Epidemiology, and End Results (SEER) registry-21, the age-adjusted incidence rate of DDLPS is 0.18 per 10,000 person-years. Incidence is higher in men than women (0.26 per 10,000 py vs 0.11 per 10,000 py) (data on file).

DDLPS is typically a high-grade tumor that metastasizes in more than 20% of cases (lungs, liver, bone, skin, or brain). The mainstay of first line (1L) therapy for advanced DDLPS remains an anthracycline-based regimen despite its moderate efficacy in this setting (objective response rate <15%; median progression-free survival: 2 to 4 months; median overall survival (OS, from initiation of 1L treatment to death or end of study): 8 to 12 months) [R21-0720]. Notably, the natural history, patient journey and treatment outcomes of this rare disease is poorly understood in Chinese patients.

Boehringer Ingelheim (BI) is currently developing BI 907828, an orally available MDM2-p53 antagonist, for treatment of DDLPS. On 22 August 2022, BI China received Clinical Trial Notification (CTN) for MDM2 DDLPS indication from China authority. In the CTN, China authority recommended BI to collect Chinese DDLPS patients' survival and other related clinical data in the real-world, to provide support for future analysis during New Drug Application. Therefore, we conduct this study to investigate the patient characteristics, current treatment patterns and outcomes in Chinese DDLPS patients.

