9.7.3. Analysis of exploratory objectives

Patient demographic, clinical characteristics and treatment outcomes will be reported for Cohort 1 and Cohort 2 (See Section 9.3.1.3 for variable definitions). If multiple records for a variable exist during the baseline period, the record closest to index will be chosen. The number of missing values will be reported for each variable, and percentages for categorical variables will be based on non-missing values. Time from diagnosis to 1L treatment, time to next treatment and duration of treatment by LOT will be estimated using KM methods to obtain median estimates with 95% CIs and IQRs.

HCRU including number of visits and days of hospitalization will be summarized as counts (n) and proportions (%). Direct medical cost will be summarized using mean, median and IQR.

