Clinical characteristics	Cohort 1	Cohort 2
Primary tumor site, N (%)		
Head or neck		
Retroperitoneum or abdomen		
Extremity		
Pelvis		
Thorax or trunk		
Other		
Missing / Unknown		
Presence of metastases, N (%)		
Yes		
No		
Missing / Unknown		
Metastatic site, N (%)		
Adrenal		
Bone		
Brain		
Distant lymph node metastases		
Liver		
Lung		
Other		
Missing / Unknown		
Number of surgeries prior to 1L		
$Mean \pm SD$		
Median (IQR)		
Min, Max		
Missing / Unknown		
Charlson comorbidity index		
$Mean \pm SD$		
Median (IQR)		
Min, Max		
Missing / Unknown		
History of smoking, N (%)		

Statistical and Epidemiological Analysis Plan (SEAP) for Observational and Non-Interventional Studies (ONIS)

Page 24 of 36

Clinical characteristics	Cohort 1	Cohort 2
Never smoker		
Former smoker		
Current smoker		
Missing / Unknown		
$BMI, kg/m^2$		
$Mean \pm SD$		
Median (IQR)		
Min, Max		
Missing / Unknown		

Abbreviations: N = number; SD = standard deviation; IQR = interquartile range; min = minimum; max = maximum; BMI = body mass index (defined as [weight in kilograms] / [height in meters]²); ECOG = Eastern Cooperative Oncology Group; 1L = first line.

Statistical and Epidemiological Analysis Plan (SEAP) for Observational and Non-Interventional Studies (ONIS)

Page 25 of 36

Table 3. Overall survival from index for Cohort 1

At 18 months, [95% CI]

At 24 months, [95% CI]

	Cohort 1	
	N=	
Overall survival from Index, months		
KM Median, [95% CI]		
IQR		
Survival rate at different time point, (100/1000 person years) At 6 months, [95% CI]		
At 12 months, [95% CI]		

Abbreviations: KM= Kaplan–Meier; CI = confidence interval; IQR = interquartile range.

Statistical and Epidemiological Analysis Plan (SEAP) for Observational and Non-Interventional Studies (ONIS)

Page 26 of 36

Table 4. Survival from initial diagnosis for Cohort 1 and Cohort 2

	Cohort 1,	Cohort 2,	
	N =	N=	
Survival from initial diagnosis, months			
KM Median, [95% CI]			
IQR			
Survival rate at different time point, (100/1000 person years) At 6 months, [95% CI]			
At 12 months, [95% CI]			
At 18 months, [95% CI]			
At 24 months, [95% CI]			

Abbreviations: KM= Kaplan–Meier; CI = confidence interval; IQR = interquartile range.

Statistical and Epidemiological Analysis Plan (SEAP) for Observational and Non-Interventional Studies (ONIS)

Page 27 of 36

Table 5.	Number	of total	lines of	f systemic	treatment

	Cohort 1,	Cohort 2,
	N=	N=
Total lines of systemic treatment		
$Mean \pm SD$		
Median (IQR)		
Min, Max		

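### As printed, the Charlson code list in Protocol Annex 3 scores the study tumour and its metastases as comorbidity, and the two cohort columns may not carry the same contribution

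*Protocol*

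**What the plan says.** Protocol Annex 3 gives ICD-9 and ICD-10 codes for 17 Charlson conditions. Two of them are cancer rows. "Any malignancy" has ICD-10 ranges that include "C58.xx, C60.x-C76.x", and "Metastatic solid tumor" has "C78.xx, C79.xx, C7B.xx". Neither row excludes the study tumour. The note under the table explains abbreviations only, and SAP Annex 1 adds nothing. The readable text gives no item weights and no rule for a patient who meets both cancer rows.

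SAP Annex 2, Table 2, has a row for the "Charlson comorbidity index", summarised by mean, SD, median, IQR, minimum and maximum, with Cohort 1 beside Cohort 2. The introduction to SAP Annex 2 says the tables are repeated for subgroups and sensitivity analyses where feasible. Protocol section 9.7.4 names metastatic and unresectable locally advanced patients among the subgroups.

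Protocol sections 9.2.2 and 9.2.3 (SAP 6.3 and 6.4) set the timing. Baseline is everything recorded before the index date. In Cohort 1 the index date is the start of first-line treatment, which follows the advanced or metastatic diagnosis. In Cohort 2 it is the date of initial DDLPS diagnosis within the identification period.

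For the definitions of the clinical characteristics, Protocol section 9.7.3 points elsewhere ("See Section 9.3.1.3 for variable definitions"), and that section is not in the public text.

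**The concern.** A comorbidity index in a cancer cohort is meant to describe what the patients have besides the cancer. A confirmed DDLPS diagnosis is required for entry, and the protocol's own background says "Liposarcoma is a malignancy of fat tissue". If the two cancer rows are applied without a carve-out, part of the score repeats the entry criterion, and a further part can follow metastatic status.

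Three comparisons could then mislead a reader of Table 2:

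- **Cohort 1 against Cohort 2.** A gap could come from stage, or from which cohort has its cancer diagnosis inside the look-back.
- **Metastatic against locally advanced subgroups.** A gap could appear with identical non-cancer comorbidity.
- **This study against others.** The level of the score cannot be interpreted without knowing whether the study cancer is counted.

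Protocol section 12 says the results may supplement regulatory submissions, so the baseline tables have readers outside the study team.

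**Working it through.** The plan states no figure on this point, so there is nothing to reproduce. The check has four steps.

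**1. Does the printed list capture the study cancer?** The documents give no ICD code for DDLPS. If it is coded in ICD-10 C48 or C49 (ICD-9 158 or 171), which is an assumption, it falls inside the malignancy row: C48 and C49 lie in C45 to C58, and 158 and 171 lie in 140 to 172. The row label supports the same reading without the assumption. C78 and C79 are outside the malignancy row and inside the metastatic row.

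**2. Is the diagnosis inside the look-back?**

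- Cohort 1: yes. First-line treatment starts after the advanced or metastatic diagnosis, and baseline is all data before that start.
- Cohort 2: not on a strict reading. The index date is the diagnosis date, and baseline is data before it, so the index diagnosis adds 0. Disease coded earlier could still count; Table 2 has a line for initial diagnosis before 2013.

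**3. What does the study cancer add to each column?** Let *m* be the weight of the malignancy row, *w* the extra score for a patient with coded metastases, and p1 and p2 the metastatic shares in Cohorts 1 and 2. Assume all disease is coded. The artificial difference in mean score, Cohort 1 minus Cohort 2, is:

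- index date inside the look-back: (m + w·p1) − (m + w·p2) = w·(p1 − p2);
- index date outside it, and no earlier cancer codes in Cohort 2: m + w·p1 − 0 = m + w·p1.

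The only metastatic share in the documents is a general one: "DDLPS is typically a high-grade tumor that metastasizes in more than 20% of cases". With assumed shares of 0.6 to 1.0 in Cohort 1 and 0 to 0.3 in Cohort 2, the first reading gives (0.6 − 0.3)w = 0.3w up to (1.0 − 0)w = 1.0w. The second gives m + 0.6w up to m + 1.0w. The metastatic and locally advanced subgroups of Cohort 1 differ by (m + w) − m = w, whatever the metastatic share. If the rows have equal weight and only one is counted, w = 0 and only *m* remains.

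**4. What share of the mean score could be study cancer?** Let D = m + p·w be the mean contribution of the study cancer, and O the mean contribution of all other conditions. The share is D/(D + O). Weights, p and O are all assumptions; p runs from 0.2 to 0.8.

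| Assumed weighting | D at p = 0.2, 0.5, 0.8 | O = 0.3 | O = 1.0 | O = 2.0 |
|---|---|---|---|---|
| 1 and 1, both rows add (m = 1, w = 1) | 1.2, 1.5, 1.8 | 80–86% | 55–64% | 37.5–47% |
| 1 and 1, only one counted (m = 1, w = 0) | 1.0, 1.0, 1.0 | 77% | 50% | 33% |
| 2 and 6, only the higher counted (m = 2, w = 4) | 2.8, 4.0, 5.2 | 90–95% | 74–84% | 58–72% |

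Examples: 1.0/(1.0 + 2.0) = 33%, and 5.2/(5.2 + 0.3) = 95%. The share is not small in any cell, but the width of the range shows that the documents do not fix its size.

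**The case against.** The strongest objection is that Annex 3 is a generic code table and the operational definition sits in a section that the public text omits. What is absent for that reason is not missing from the plan, and that section may exclude the study cancer. This stands: the documents do not show that the study cancer will be counted, only that the printed list would count it.

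A reader might also infer stronger claims that the documents do not support:

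- *That the index mostly restates the disease.* With no weights, hierarchy rule or comorbidity rates, the share falls on either side of one half.
- *That every patient scores on a cancer row.* Cohort 2's index diagnosis may lie outside the look-back. A metastatic patient is defined by diagnosis or metastatic sites, which need not match the codes in the Charlson row.
- *That the score cannot describe comorbidity.* Fifteen of the 17 conditions are not cancer and still contribute. A constant shared by all patients moves the mean and median but leaves the spread unchanged.

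Finally, the consequence is limited. Protocol section 9.3 and SAP section 7 plan no formal comparison of groups, and no readable passage uses the index in the survival or treatment-pattern estimates. Table 2 also reports stage, presence of metastases and metastatic site, so a reader can see a stage difference directly. This stands and keeps the point minor. It also means that taking the study cancer out of the index loses no information about it.

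**Conclusion.** The point holds for the printed list. Applied as written, Annex 3 gives Cohort 1 patients with coded disease a score for the study cancer, and the score rises with metastatic status whenever w is above 0. The Table 2 Charlson figures would then partly reflect disease stage. Between the cohorts, the artificial difference is w·(p1 − p2) or m + w·p1, depending on whether the index date is in the look-back, so the two columns may not be comparable. No value in points can be given, because the readable text does not state m and w; the 33% to 95% range rests wholly on assumed inputs.

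The conclusion is conditional on the omitted definition not already excluding the study cancer. It touches one descriptive row and its subgroup and sensitivity replicates. In the readable text, overall survival and treatment patterns are unaffected.

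**What to change.** In Protocol Annex 3 and SAP Table 2:

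- compute the index without the metastatic row, because nothing printed there separates metastases of the study tumour from those of another cancer;
- keep the malignancy row but exclude the study tumour from it, and list the codes treated as the study tumour;
- label the result *Charlson index excluding study cancer*;
- report other prior malignancy as a separate yes/no row, so that genuine second cancers stay visible;
- state the item weights, and whether records on the index date belong to the look-back.

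If section 9.3.1.3 already does this, align Annex 3 with it by a one-line note.

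The cost is an edit to two rows of a code list and one added table row. The downside is that the score becomes less comparable with published totals that include cancer.
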